2.2. Statistical methods

2.2.1. General considerations

The following descriptive statistics will be provided depending on the nature of considered data:

- **Qualitative data:** number of observed values, number and percentage of patients per class;
- **Quantitative data:** number of observed values, mean and standard deviation, median, first and

Study Code: GNC-401
Version No: 3.0
Version Date: 2020-05-01

third quartiles, minimum and maximum;

- **Survival data (time to event occurrence or to censoring):** total number of patients, total number and percentage of patients having an event, number of patients at risk, number of patients with censored data, number of patients with event of interest.

The type I error will be set at $\alpha = 5\%$ two-sided.

The treatment effect (temelimab versus placebo) will be estimated as well as its precision: estimate of the difference, standard error (SE) of the estimate and two-sided 95% confidence interval (CI) of the estimate.

In case of formal comparison between treatment groups, the two-sided p-value associated with the treatment effect will also be provided.

All inferential analyses are considered as exploratory in order to have a first estimation of treatment effect. Consequently, no method to handle with multiplicity issues is needed.

2.2.2. Study patients:

Demographic data and other baseline characteristics will be described by treatment group, to assess their comparability, and overall in the RS population. The main patients' characteristics will also be described for SS population.

Disposition of patients, including reasons for withdrawal, protocol deviations, extent of exposure and treatment compliance, as well as concomitant treatments will be described in the RS population.

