2.2.3. Safety analysis

Safety and tolerability of temelimab and placebo will be assessed in each treatment group in the safety population.

AE summaries will include all AEs starting on or after study day 1 (i.e. on the day of or following the day of first study treatment administration) and starting before the end of study visit, i.e. 4 weeks after the date of last study treatment administration.

A Summary of AEs (number and % of patients, number of AEs) and summarized by System Organ Class (SOC) and Preferred Term (PT) will be tabulated by treatment group and overall for patients with:

- at least one treatment-emergent adverse event (TEAE),
- at least one related treatment-emergent adverse event (TEAE),
- at least one severe treatment-emergent adverse event (TEAE),
- at least one severe related treatment-emergent adverse event (TEAE),
- at least one serious TEAE,
- at least one serious TEAE related to the study treatment,
- a TEAE leading to treatment discontinuation,
- a related TEAE leading to treatment discontinuation,
- a TEAE leading to death.

Study Code: GNC-401
Version No: 3.0
Version Date: 2020-05-01

AEs will be summarized by presenting the number and percentage of patients having at least one AE and by number of AEs, overall and by treatment group. Data will be presented by SOC and PT using the latest version of MedDRA. A patient with multiple occurrences of the same PT will be counted only once in the AE category.

Separate AE summaries will be presented by SOC, PT, and severity. In the summaries presented by severity, all AEs will be pooled. Specific tables will summarize related AEs to temelimab.

Written narratives will be produced for all SAEs.

Adverse events/SAEs occurring after signing the Inform Consent Form (ICF) but before starting study treatment, including those observed in patients included but never treated with the IMP, will be listed separately from those occurring after treatment start.

Adverse events/SAEs occurring after 4 weeks after the date of last study treatment administration will be also listed separately.

Laboratory data analysis:

The summaries will include all laboratory assessments collected during the study.

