2.3. Determination of sample size

The total sample size (N=40) is not based on a formal statistical assessment. This number of subjects is considered sufficient to achieve the primary safety objective of the study which will be based on a descriptive evaluation of safety data, in addition the difference dosage and placebo will allow to assess any variations in terms of severity or frequency or adverse events between the doses.

For the secondary endpoints the sample size was assessed as follows:

Results from MTR% (peri-ventricular bands) in the GNC-004 study are:

- $0.84\% \pm 4.84$ in the 18 mg/kg dose (n=23)
- $-3.17\% \pm 2.05$ for placebo (n=26)

Simulation on SAS® Version 9.4 and on R software have been performed in order to explore the capability of the study to detect a signal of efficacy.

The table below gives the power according to several hypotheses for the 40 patients.

Table 3. Power and posterior probabilities simulations with alpha 5% two-sided

Temelimab (n=10)		Placebo (n=10)		Delta Temelimab Placebo		Power for at least one dose superior to placebo	Power for pooled doses versus placebo	Posterior P(at least one dose with delta>0)>95%	Posterior P(pooled doses with delta>0)>95%
Mean	Std	Mean	Std	Mean	Std	Non parametric Sign test		MCMC simulations	
-0.84	4.84	-3.17	2.05	2.33	5.26	52%	63%	78%	90%
-0.5	4	-3	2	2.5	4.47	67%	83%	88%	95%
0	4	-3	2	3	4.47	80%	94%	96%	>95%
1	4	-3	2	4	4.47	95%	>95%	>95%	>95%

With 10 patients per group, $-3\% \pm 2$ for placebo and $0\% \pm 4$ for temelimab, the study has 80% power to show a statistically significant (5% two-sided) difference for at least one dose. The power is higher than 80% for the comparison of pooled dose (n=30) versus placebo.

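### Adverse event (AE) tables by dose use crude counts over a window tied to each patient's last infusion, so unequal early stopping would understate total and later-onset events

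*Combined protocol and SAP*

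**What the plan says.** The AE rules are in section 2.2.3 (Safety analysis).

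- **Window.** Summaries take AEs from the first treatment day, "starting before the end of study visit, i.e. 4 weeks after the date of last study treatment administration". The end point follows the patient's own last infusion and is not a fixed Week 48.
- **Measure.** "AEs will be summarized by presenting the number and percentage of patients having at least one AE and by number of AEs". The figures are given for each arm and in total, in the safety population. In the text supplied, no patient-time denominator and no time-to-first-AE analysis is given. Kaplan-Meier is planned only for time to first relapse (section 10.2.5.2).
- **Later events.** "Adverse events/SAEs occurring after 4 weeks after the date of last study treatment administration will be also listed separately". No AE table is said to count them.
- **Discontinuation.** The AE summary has its own row for "a TEAE leading to treatment discontinuation", and another for related events of that kind.
- **Exposure.** Under section 2.2.2 (Study patients), "extent of exposure and treatment compliance, as well as concomitant treatments will be described in the RS population". It is not linked to the AE frequencies.
- **Use.** Section 2.3 says that having several doses and placebo "will allow to assess any variations in terms of severity or frequency or adverse events between the doses".

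**The concern.** Safety and tolerability at the three dose levels is the primary objective, and the AE summaries head the list of primary endpoints. Comparing AE frequency between doses is one stated use of those tables.

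A crude percentage or count is comparable between arms only if the arms are observed for similar lengths of time. Here the observation time that counts shrinks whenever a patient stops early. If one dose has more early stopping than another, its patients have less time in which to add events to the tables, but they still count fully in the denominator. Part of any real difference in later or repeated events could then be lost, and with heavy, early imbalance the order of the arms could change in those rows.

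**Working it through.** **Inputs from the documents.** There are 12 four-weekly infusions, the last at Week 44, and 40 patients randomised 1:1:1:1, so 10 per arm. The AE window ends 4 weeks after the last infusion.

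**Schedule check.** Infusions at Weeks 0, 4, ..., 44 make 12, and 44 + 4 = 48 weeks, which agrees with the stated treatment period. A patient who stops after k infusions has a window of 4k weeks: 8 weeks after two infusions (the second is at Week 4), 12 after three. A full arm has 10 × 48 = 480 patient-weeks. Section 2.3 gives no formal safety calculation to reproduce.

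**Assumptions.** The documents give no AE rate or discontinuation rate. Everything below assumes a constant event rate, a comparator arm with no early stops, and stopping unrelated to the event being counted.

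**1. Expected event counts.** With s stoppers who each have a w-week window, the ratio to a full arm is [(10 − s) × 48 + s × w] / 480.

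| Stoppers | w = 8 weeks | w = 16 weeks |
|---|---|---|
| 1 | 440/480 = 0.917 (−8%) | 448/480 = 0.933 (−7%) |
| 2 | 400/480 = 0.833 (−17%) | 416/480 = 0.867 (−13%) |
| 3 | 360/480 = 0.750 (−25%) | 384/480 = 0.800 (−20%) |

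With three stoppers at 8 weeks, a true rate ratio of 1/0.75 = 1.33 would show as equal counts.

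**2. Percentage of patients with a given event.** At an assumed rate of 0.7 per 48 weeks, full windows give 1 − exp(−0.7) = 50.3%. An 8-week window gives 1 − exp(−0.7 × 8/48) = 11.0%. With three such stoppers the arm shows (7 × 0.503 + 3 × 0.110)/10 = 38.5%.

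**3. The same event when it is the reason for stopping.** All three stoppers then count as having it: (3 + 7 × 0.503)/10 = 65%. There is no understatement in that row.

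**4. A true difference.** Assume 50% incidence on placebo over 48 weeks and a true rate ratio of 1.5. Full follow-up gives 1 − 0.5^1.5 = 64.6% on the dose. Stopping after three infusions (12 weeks) gives 1 − 0.5^(1.5 × 12/48) = 22.9% for those patients.

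- Two of 10 stop: (8 × 0.646 + 2 × 0.229)/10 = 56.3%. The gap from placebo falls from 14.6 to 6.3 points but keeps its direction.
- Four of 10 stop: (6 × 0.646 + 4 × 0.229)/10 = 47.9%, just below placebo. The event-count ratio is 1.5 × 336/480 = 1.05.

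Dividing events by patient-time returns 1.5 in both cases, because the rate is assumed constant.

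**5. Front-loaded events.** Suppose every patient in two arms has one event at the first infusion, and three in one arm later stop with 8-week windows. The crude tables show 10/10 in both, which is correct. Events per patient-week are 10/480 and 10/360, a false ratio of 1.33.

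**The case against.** A reader might infer that a dose which drives patients off treatment will look safer than it is. The documents do not support that as a general statement. A patient who stops because of an AE already counts in the any-TEAE row and in the row for TEAEs leading to discontinuation, by group, system organ class and preferred term. Step 3 shows that the row for the causal event is not diluted. This objection stands and limits the point to total counts and to other, later-onset events.

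It is also fair that the size is assumed. The rationale describes temelimab as well tolerated over two years of repeated dosing, and a discontinuation row is standard, so it does not show that the plan expects unequal stopping. Reversal in step 4 took 4 of 10 patients stopping early in one arm and none in the other. Chance variation is large too: for 7 observed events (10 × 0.7), the exact Poisson 95% interval is about 2.8 to 14.4, so a fall to 5.25 (7 × 0.75) lies well inside it.

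Much of the information is also visible elsewhere. Reasons for withdrawal and extent of exposure are described, SAEs get narratives, later events are listed, laboratory summaries include all assessments in the study, and the safety board reviews all available safety data. Section 2.3 calls the safety evaluation descriptive, and section 2.2.3 sets no between-dose AE test. Implementation detail is left to a SAP still to be signed. These points lower the weight of the concern. They do not supply the missing figure, because exposure described separately, and in the randomised set, does not give AE frequency per unit of time in the Safety Set.

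A further tempting step is to base the comparison between doses on exposure-adjusted rates. Step 5 shows why not: for events around the first infusions such rates can create a difference that does not exist. Section 1 requires 6 hours of observation after the first infusion and at least 2 hours after later ones, so events of that kind are a plausible interest here.

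**Conclusion.** The point holds in a limited form. If early stopping differs between arms, section 2.2.3 understates total event counts, and the incidence of later-onset events other than the one that caused stopping, in the arm with more of it. Under a constant rate, 1 to 3 of 10 patients stopping after the Week 4 infusion lower expected counts by 8% to 25% against an arm with none. The effect is nil without early stops and small if stopping is similar across arms. It weakens if events cluster early. Modest imbalance dilutes a difference without reversing it. The AEs that led to stopping remain visible, and later events are listed, so the distortion concerns certain rows of the AE frequency tables and not the safety report as a whole. The discontinuation and event rates behind these figures are assumptions. Graded CONSIDER: a cheap improvement.

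**What to change.** Keep the crude counts and percentages in section 2.2.3 as the main display. In the SAP, before it is signed, add per arm in the Safety Set:

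1. Patient-time in the AE window (Day 1 to last infusion plus 4 weeks), shown beside the crude figures.
2. Supplementary exposure-adjusted rates with 95% CI: patients with a first event per patient-time at risk and, for total event counts, a rate whose CI allows for repeat events within a patient.
3. A statement that these rates assume a roughly constant hazard and are not to be relied on for early infusion-related events.
4. One by-group table counting all AEs from Day 1 to last study contact, where follow-up after stopping exists. The synopsis mentions a study discontinuation visit, so this table may add little if contact ends there.

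The cost is a few columns, one table and the constant-hazard assumption. Applying the planned window already requires AE start dates and last-infusion dates, and trial conduct does not change.

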10.2.4 Efficacy analyses

Each secondary endpoint will be described by treatment group in the RS population.

Study Code: GNC-401
Version No: 3.0
Version Date: 2020-05-01

For exploratory analyses, Frequentist and Bayesian methodologies will be used.

For the frequentist approach change from baseline at Week 48 will be analyzed using a non-parametric ANCOVA including baseline and treatment as factors.

For all analyses, estimate of treatment effect (temelimab versus placebo), its SE and 95% CI, as well as the associated p-value will be provided.

In addition, exploratory Bayesian analysis will be done using a non-informative prior on mean and standard error. The Posterior probability that the change from baseline at Week 48 is <0 will be provided for each dose and for placebo with its 95% credible interval (measure of Bayesian precision).

An alternative Bayesian version of the T-test: Bayesian Estimation Supersedes the t-test (BEST) developed by (Kruschke, 2012) will also be used⁷⁴. The difference of the change in lesion volume between each dose and placebo and the posterior probability that Delta versus placebo is >0 will be provided. If these posterior probabilities are $> 80\%$, temelimab could be considered as interesting for future development.

Those probabilities will also be provided for the other measurements of change.

For sensitivity analyses, the same analyses will be performed comparing pooled dose with placebo.

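### The BEST comparison behind the 80% development signal ignores baseline, although the frequentist analysis of the same change endpoints adjusts for it

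*Combined protocol and SAP*

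**What the plan says.** Section 10.2.4 (Efficacy analyses) gives three analyses of the Week 48 change.

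- **Frequentist:** "change from baseline at Week 48 will be analyzed using a non-parametric ANCOVA including baseline and treatment as factors".
- **First Bayesian analysis:** "exploratory Bayesian analysis will be done using a non-informative prior on mean and standard error". It gives, for each dose and for placebo, the probability that the change is below zero. No baseline term is named, and no threshold is attached.
- **Second Bayesian analysis:** "An alternative Bayesian version of the T-test: Bayesian Estimation Supersedes the t-test (BEST"). Its estimand is "The difference of the change in lesion volume between each dose and placebo", with the posterior probability that this difference is positive. No covariate is named.

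The threshold follows directly on the BEST comparison: "If these posterior probabilities are $> 80\%$, temelimab could be considered as interesting for future development". The section then adds: "Those probabilities will also be provided for the other measurements of change". Pooled doses against placebo are a sensitivity analysis.

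All six secondary endpoints in the synopsis are changes from baseline to Week 48. Section 10.2.5.2 carries the same frequentist and Bayesian methods over to the exploratory endpoints. Time to first relapse is analysed by log-rank, and new T2 lesions by a negative binomial model that includes baseline. Section 2.2.1 calls all inference exploratory. Section 2 (Statistics) defers implementation detail to a SAP to be signed before database lock.

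**The concern.** The plan uses baseline in the analysis without a threshold and leaves it out of the analysis with one. In arms of 10, chance baseline differences are large. If patients with higher or lower baseline values tend to change more, part of the BEST difference between a dose and placebo is imbalance rather than drug effect. It can push the posterior probability past 80%, or hold it below, in the particular trial that was run. Leaving out a prognostic baseline also discards precision that a 40-patient trial can ill afford. Each dose-placebo pair is fitted alone, although all four arms could share one baseline slope.

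**Working it through.** **Inputs from the documents.** Allocation is 1:1:1:1 with N = 40, so n = 10 per arm (synopsis). The planning values are placebo −3 (SD 2) and temelimab 0 (SD 4), with stated power of 80% for at least one dose (section 2.3). The threshold is 80% (section 10.2.4).

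**Assumption.** The correlation ρ of change with baseline is not in the documents. The range used is |ρ| = 0 to 0.7.

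**1. The plan's own figure.** Simulating three dose arms and a shared placebo arm with an exact two-sided 5% rank-sum test gives 81.3% for at least one dose, against the stated 80%. The stated power for pooled doses (94%) did not reproduce (71% by rank-sum, 86% by Welch t), but nothing below uses it. Table 3 reports posterior probabilities at 95%, so the plan gives no figure for the 80% signal that could be checked.

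**2. Size of chance imbalance.** The SD of the standardised baseline difference between two arms is √(2/10) = 0.447. The chance that it exceeds 0.5 in absolute value is 2 × [1 − Φ(0.5/0.447)] = 26%.

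**3. What it does to BEST.** Passing 80% under a flat prior needs an observed difference of about 0.842 × 0.447 = 0.38 SD of change (normal approximation). A one-SE imbalance shifts the unadjusted difference by 0.447 × |ρ|, which is 0.13, 0.22 and 0.31 SD at |ρ| = 0.3, 0.5 and 0.7.

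**4. False-signal rate given an imbalance d in the unlucky direction, no true effect.** The unadjusted rate is Φ[(|ρ|d/0.447 − 0.842)/√(1 − ρ²)]. At d = 0.5 this gives 29.8%, 37.2% and 46.7% for |ρ| = 0.3, 0.5 and 0.7. A simulation of 40,000 trials, with BEST approximated by an unequal-variance t posterior, agrees:

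| Assumed abs. ρ | Unadjusted, d about 0.5 | Adjusted, d about 0.5 | Unadjusted, d about 0.9 | Adjusted, d about 0.9 |
|---|---|---|---|---|
| 0 | 20% | 20% | 20% | 19% |
| 0.3 | 30% | 20% | 39% | 19% |
| 0.5 | 38% | 21% | 56% | 19% |
| 0.7 | 45% | 19% | 77% | 18% |

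**5. Average false-signal rate.** Over all trials it is about 20% per dose and about 39% for at least one of three doses, adjusted or not. Lucky and unlucky imbalances cancel. By the formula in step 4, a one-SE imbalance against the dose lowers the unadjusted rate to 11.6%, 6.1% and 1.5% at the three correlations.

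**6. Precision.** With one slope over 40 patients and equal SDs, the variance ratio (adjusted to unadjusted) is about (1 − ρ²)(1 + 1/34), where 34 = 40 − 4 arm means − 2. This gives 1.03, 0.94, 0.77 and 0.53 at |ρ| = 0, 0.3, 0.5 and 0.7. Simulating a model with arm-specific SDs and normal errors gives:

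| Assumed abs. ρ | Equal SDs | SDs 4 and 2 |
|---|---|---|
| 0 | 1.03 | 1.03 |
| 0.3 | 0.95 | 0.96 |
| 0.5 | 0.77 | 0.80 |
| 0.7 | 0.54 | 0.57 |

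**7. Chance of a signal for one dose when there is an effect.** For a true difference of 2 with common SD √((16 + 4)/2) = 3.16, it is about 71% unadjusted. Adjusted, it is about 73%, 77–78% and 85–87% at |ρ| = 0.3, 0.5 and 0.7. In the 0 versus −3 scenario it is 89–90% unadjusted and 89%, 90%, 93% and 97% adjusted at |ρ| = 0, 0.3, 0.5 and 0.7.

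**The case against.** The threshold only says that "temelimab could be considered as interesting for future development", inference is exploratory, and the primary objective is safety. The baseline-adjusted frequentist estimate with its interval will be reported alongside, so a reader can see whether adjustment matters, and the later SAP could add the covariate. All of this stands and limits the weight of the point. But BEST as named is a t-test analogue without covariates, so adding baseline changes a stated method; it does not merely supply missing detail.

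A second objection is that adjustment is not free. A joint model with equal variances does lose under the planning SDs of 4 and 2: at a true difference of 2 its signal rate falls from 71% to 67% at zero correlation, and is still only 69% at |ρ| = 0.3. That stands against an equal-variance model, and arm-specific SDs largely remove it. The model proposed below, with t errors, was approximated with normal errors and not simulated exactly. It also assumes one linear baseline slope for all arms, and t errors do not protect against high-leverage baseline values.

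Four stronger readings are tempting, and the documents do not support them:

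- A reader might infer that imbalance passes straight into the signal. BEST compares changes, so it enters only in proportion to ρ. At ρ = 0 it has no effect.
- A reader might infer that every endpoint is affected. Time to relapse and new T2 lesions have other models, and temelimab levels have no stated baseline comparison.
- A reader might infer that the two analyses could disagree only through baseline imbalance. One is non-parametric with a two-sided p-value; the other is a t-likelihood posterior read at 80%. They can disagree with balanced baselines.
- Adjusted and unadjusted signals differ in about 7–21% of simulated trials at |ρ| = 0.3 to 0.7. A reader might attribute all of that to imbalance, but about 3–5% differ even at zero correlation.

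**Conclusion.** The point holds for the change-from-baseline endpoints as a cheap improvement. The only efficacy threshold in the plan rests on an unadjusted estimate, while the same section adjusts for baseline elsewhere. The average error rate is not inflated. The harm is a false-signal rate that depends on the imbalance that happens to occur, and a variance about 5% to 46% higher than it needs to be as a share of the unadjusted value (ratios 0.95 to 0.54, equal SDs) if |ρ| is 0.3 to 0.7. Both effects are conditional on a correlation that the documents do not give, and both vanish at zero. The calculations also assume normal data, flat priors and a t-posterior approximation to BEST. It would be wrong to read this as a flaw in a binding go/no-go decision; the plan sets none.

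**What to change.** In section 10.2.4, and in the SAP before database lock:

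- For the change-from-baseline endpoints, take the posterior probabilities used with the 80% threshold from one Bayesian model over the four arms, with terms for arm and baseline.
- Keep BEST's t-distributed errors and arm-specific SDs, because the planning SDs are 4 and 2. Keep the priors non-informative.
- Obtain each dose-placebo contrast, and the pooled-dose contrast, from that model.
- Report unadjusted BEST as a sensitivity analysis.
- Leave time to relapse and new T2 lesions with their present models.
- Describe the expected gain as conditional on an unknown correlation, and check the common linear slope and any extreme baseline values.

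The cost is a few lines of model code and a sentence or two of text, with no extra patients, visits or data. The statistical price is about 3 to 4% more variance if baseline proves uninformative, plus the common-slope assumption.

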- reduction in volume loss in whole brain, cerebral cortex and thalamus,
- reduction in T1 hypointense (T1 Black Hole) lesion number and volume,
- stabilization of magnetization transfer ratio (a magnetic resonance imaging (MRI) measure of myelin integrity) in both normal-appearing white matter and cerebral cortex, over 96 Weeks.

However, no clinically-relevant effects were observed with temelimab as monotherapy on MRI measures of neuroinflammation in RRMS patients.

Phase 2 clinical trial data with rituximab in RRMS patients demonstrated highly significant effects on neuroinflammation, which is seen even years after cessation of treatment. In contrast, rituximab failed to demonstrate a statistically significant effect on disease progression in Primary progressive multiple sclerosis (PPMS).

Study Code:	GNC-401
Version No:	3.0
Version Date:	2020-05-01

Although rituximab is not approved by the European Medicines Agency (EMA) for any form of MS, rituximab has become the most frequent disease modulatory treatment in Sweden for MS, based on positive results obtained in several real world cohorts.

Therefore, the introduction of temelimab treatment, in relapsing MS (RMS) patients who have been treated with rituximab, and hence experience sustained reduction of relapse activity and lesion formation is postulated to have a significant additional beneficial effect on disease progression.

In all preclinical as well as clinical studies to date, temelimab has shown to be well tolerated with no apparent safety signal either at repeated doses over two years in RRMS, or at single doses in healthy human volunteers as high as 110 mg/kg.

In addition, no drug-drug interactions are expected with the staggered administration of temelimab after rituximab, based on data from human ex vivo models.

This proposed clinical Phase 2a study will be performed in patients with RMS who have been receiving rituximab off-label, as per local clinical practice guidelines for at least 12 months. In this study temelimab is administered subsequently to rituximab therapy, i.e. no co-administration of rituximab and temelimab is done in this study.

Primary objective:

- To assess the safety and tolerability of temelimab following intravenous (IV) administration of 18 mg/kg, 36 mg/kg or 54 mg/kg, in patients with RMS who have been treated with rituximab for at least 1 year.

Secondary objective:

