- The urine dipstick pregnancy test indicates a negative result, but an early pregnancy (\leq 2 weeks from conception) is suspected by the investigator based on anamnestic or clinical elements and cannot be ruled out by further investigations

Investigational product(s), dosage, administration: Temelimumab 18 mg/kg, 36 mg/kg, 54 mg/kg or matching placebo will be given as monthly (4-weekly) intravenous (IV) infusions over 48 weeks (12 administrations in total).

Study endpoints: Primary endpoints:

- Overall Summary of Adverse Events
- AEs by Primary SOC and PT
- SAE by Primary SOC and PT
- Physical Examination: Shift from Baseline to worst post-dose result by Body System
- ECG Interpretation: Change from Baseline to Week 48 and Summary Statistics for change from Baseline to Week 48
- Vital Signs: Summary Statistics For Change From Baseline By Follow-Up Visit

Study Code: GNC-401
Version No: 3.0
Version Date: 2020-05-01

- Concomitant Medications by WHO ATC Level Class 1 and WHO ATC Level Class 2
- Hematology: Normal Range Shifts from Baseline by Follow-Up visit
- Clinical Chemistry (including C-reactive protein): Normal Range Shifts from Baseline by Follow-Up Visit -Safety Set
- Coagulation: Normal Range Shifts from Baseline by Follow-Up Visit - Safety Set
- Urinalysis: Normal Range Shifts from Baseline by Follow-Up Visit

Secondary endpoints:

- Change in magnetization transfer (MTR) in periventricular normal-appearing white matter (NAWM) at week 48 compared to baseline
- Change in magnetization transfer (MTR) in cerebral cortex at week 48 compared to baseline
- Change in T1 lesion volume at week 48 compared to baseline
- Change in T2 lesion volume at week 48 compared to baseline
- Change in brain parenchymal volume fraction at week 48 compared to baseline
- Change in thalamic volume fraction at week 48 compared to baseline

Exploratory endpoints

- An “Overall Disability Response Score” (ODRS) which takes into consideration EDSS, T25FW, dominant and non-dominant 9-HPT, accounting for Worsening and Improvement on Respective Components from Baseline to Week 48
- Event of relapse, as measured by time to relapse and annual relapse rate (ARR)
- Change in Symbol Digit Modalities Test (SDMT) Score at Week 48 compared to Baseline
- Change in Quality of Life (EQ-5D) at Week 48 compared to Baseline.
- Number of new T2 lesions at Week 48
- Change in cortical thickness at week 48 compared to baseline

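### The 80% development benchmark is written for an unspecified lesion volume, while the planning simulations are for periventricular MTR at a 95% cut-off

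*Combined protocol and SAP*

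**What the plan says.** Section 10.2.4 (Efficacy analyses) plans a Bayesian comparison of each dose with placebo by the BEST method. The quantity named is "The difference of the change in lesion volume between each dose and placebo". The summary to be reported for this quantity is worded as follows: "the posterior probability that Delta versus placebo is >0 will be provided". The benchmark comes next. When the probabilities pass 80%, the plan's conclusion is that "temelimab could be considered as interesting for future development". For every other endpoint the section says only this: "Those probabilities will also be provided for the other measurements of change". No threshold is repeated there. Pooled doses against placebo are a sensitivity analysis.

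The Synopsis lists two lesion-volume secondary endpoints, one for T1 and one for T2 ("Change in T2 lesion volume at week 48 compared to baseline"). It also lists MTR in periventricular NAWM and MTR in cerebral cortex.

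Section 2.3 bases its planning for the secondary endpoints on MTR alone: "Results from MTR% (peri-ventricular bands) in the GNC-004 study are" the starting point, and every row of Table 3 is on that scale. The posterior columns of Table 3 use a 95% cut-off.

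**The concern.** The threshold and the planning do not meet. The endpoint that carries the 80% figure has no assumed effect, no SD and no simulation. The endpoint that has all three carries no threshold. The cut-off that was simulated (95%) is not the one that will be applied (80%).

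Three choices are also left open: T1 or T2; whether the 80% extends to MTR; and whether one dose, all doses or the pooled doses must pass. If they stay open until the data are seen, the benchmark can be read to suit the result and loses most of its value as a criterion fixed in advance.

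The direction is a further sign that the wording was not matched to the endpoint. In Table 3 Delta is temelimab minus placebo, so a value above 0 is benefit for MTR. Under that definition a value above 0 for lesion volume means more lesion growth on temelimab. Section 10.2.4 does not redefine Delta.

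**Working it through.** **Inputs.** From Section 2.3: "With 10 patients per group, $-3\% \pm 2$ for placebo and $0\% \pm 4$ for temelimab" (Table 3 row 3); row 1 has temelimab -0.84 (SD 4.84) and placebo -3.17 (SD 2.05); three doses share one placebo arm; alpha is 5% two-sided. From Section 10.2.4: pass if the posterior P(Delta>0) exceeds 0.80. The documents give no lesion-volume mean or SD.

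**Step 1: reproduce the plan's figure.** Simulation of three doses of 10 against one placebo arm of 10, two-sample rank-sum test, no multiplicity adjustment, success if any dose is superior (10,000 trials per row):

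| Table 3 row | Stated power, at least one dose | Recomputed |
|---|---|---|
| 1 | 52% | 54% |
| 2 | 67% | 69% |
| 3 | 80% | 82% |
| 4 | 95% | 95% |

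The any-dose power column reproduces within 2 points. The pooled power column did not reproduce (row 3: stated 94%; rank-sum 70%, Welch t 85%), so the pooled figures below deserve more caution.

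**Step 2: the posterior.** With flat priors,

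P(Delta>0 | data) ≈ F_ν[(mean_T − mean_P) / √(s_T²/n_T + s_P²/n_P)],

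where F_ν is the t distribution function with Welch-Satterthwaite degrees of freedom, and n is 10 per arm (30 for the pooled doses). This approximates the planned analysis and is not the full BEST model. At the 95% cut-off it gives an any-dose result 3 to 7 points below the stated column (row 1: 71% against 78%; row 2: 84% against 88%; row 3: 93% against 96%).

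**Step 3: hand check of one dose at 80%.** P(pass) ≈ Φ(δ/SE − 0.842).

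- Row 3: δ = 0 − (−3) = 3; SE = √(16/10 + 4/10) = 1.414; 3/1.414 − 0.842 = 1.28; Φ = 90%.
- Row 1: δ = −0.84 + 3.17 = 2.33; SE = √((23.43 + 4.20)/10) = 1.662; 2.33/1.662 − 0.842 = 0.56; Φ = 71% (simulation 70%).
- No effect: Φ(−0.842) = 20%, which is 1 − 0.80 by construction.

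**Step 4: simulated pass rates for the 80% rule on MTR.**

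| Assumption | One given dose | At least one | All three | Pooled |
|---|---|---|---|---|
| Row 3 | 90% | 99.5% | 74% | 99% |
| Row 1 | 70% | 96% | 38% | 90% |
| No effect, equal SDs | 20% | 39% | 5% | 20% |
| No effect, SD 4 and 2 | 20% | 45% | 2% | 20% |

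Section 2.3 gives the 18 mg/kg result as +0.84 in the text, while row 1 uses −0.84. With +0.84, one dose passes in 94% of trials and at least one in 99.9%.

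The any/all choice matters: with no effect and equal SDs, the same rule passes in 39% or 5% of trials. Table 3's 95% columns cannot stand in for the 80% rule either: in row 3 one dose passes the 95% cut-off in 65% of trials and the 80% cut-off in 90%.

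**Step 5: lesion volume, on an assumed scale.** Assume a true reduction of 0.5 SD (range 0.3 to 0.8 SD), equal SDs, and Delta as dose minus placebo:

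| Direction of the rule | One dose passes | At least one passes |
|---|---|---|
| Delta > 0 as written | 2.5% (6.2% to 0.4%) | 6% (15% to 1%) |
| Sign reversed so that > 0 is benefit | 61% (43% to 82%) | 84% (68% to 96%) |

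A lesion-volume rule therefore needs its direction defined before it can be used.

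**The case against.** The strongest reply is that this is a soft benchmark in a safety study. The wording is that temelimab could be considered interesting; Section 2.2.1 calls all inferential analyses exploratory; and Section 2.3 says the total of 40 has no formal statistical basis. MTR is not left out: its posteriors, estimates, intervals and p-values will all be reported. A SAP signed before database lock is promised and could settle the details. All of this stands, and it limits the weight of the point. It does not supply the missing endpoint, direction, dose rule or operating characteristics.

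A reader might go further and infer that lesion volume is something temelimab is not expected to move, so that a drug active on MTR would pass only at the chance rate. The documents do not support that. The Short Rationale lists a reduction in T1 black-hole number and volume among the earlier findings. Its statement that "no clinically-relevant effects were observed with temelimab as monotherapy on MRI measures of neuroinflammation in RRMS patients" does not name those measures, so applying it to T2 volume is inference. The 20% pass rate applies to lesion volume only if its true effect is exactly zero, which the documents do not say.

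Nor do the documents say that failing the benchmark ends development.

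**Conclusion.** The mismatch is real. The only numerical development threshold is tied to an unspecified lesion volume, while the planned endpoint, periventricular MTR, has no threshold and was simulated at a different cut-off. On MTR the 80% rule separates an active drug from an inactive one reasonably well for a single dose (about 90% or 70% against 20%). It does so less well if any one dose suffices (99.5% or 96% against 39%). None of this is in the plan. The figures rest on normal data, 10 patients per arm, Table 3's means and SDs, and a flat-prior approximation to BEST. The lesion-volume figures rest on assumed effects and show only how much the direction matters.

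That the positive direction fits MTR suggests that lesion volume may be a drafting slip, but the documents cannot settle this. The point is worth correcting before unblinding; it does not threaten the safety objective.

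**What to change.** In Section 10.2.4 or the SAP, before unblinding:

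1. Write the 80% benchmark for change in MTR in periventricular NAWM at Week 48, the listed endpoint closest to the periventricular-band data behind Table 3. Define Delta as temelimab minus placebo, so that above 0 means benefit.
2. State whether any dose, all doses or the pooled doses must pass.
3. Add the operating characteristics of the 80% rule to Table 3, including a no-effect row, run with the model that will be used. The figures above indicate what to expect.
4. Keep T1 and T2 lesion volume as separately named supportive measures. If a lesion-volume rule is wanted instead, name T1, define the direction of benefit and simulate it under stated assumptions.

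This takes a few sentences and one simulation. The downside is that the sponsor commits to one decision endpoint for a benchmark that remains exploratory and non-binding.
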